12.7.4.2 Chemistry

Clinical Chemistry/Biochemistry parameters include Sodium, Potassium, Urea Nitrogen (BUN), Urea, Creatinine, Calcium, Total Protein, Albumin, Bilirubin (Total), Direct Bilirubin, Indirect Bilirubin, Aspartate Aminotransferase (AST; SGOT), Alanine Aminotransferase (ALT; SGPT), Gamma Glutamyl Transferase (GGT), Lactate Dehydrogenase (LDH), Alkaline Phosphatase (ALP), Magnesium, C-Reactive Protein (CRP).

Chemistry parameters will be summarized (n, mean, SD, median, Q1, Q3, minimum and maximum), including change from baseline at each visit. In addition, shift tables summarizing the shift including baseline, minimum and maximum post-baseline values and last value will be presented. In addition, all parameters will be presented in a line plot for all planned visits.

12.7.4.3 Coagulation

Coagulation parameters include Activated Partial Thromboplastin Time (aPTT), Prothrombin Intl. Normalized Ratio (INR), Prothrombin Time (PT).

All parameters will be summarized (n, mean, SD, median, Q1, Q3, minimum and maximum), including change from baseline at each visit. In addition, shift tables summarizing the shift including baseline, minimum and maximum post baseline values and last value will be presented. In addition, all parameters will be presented in a line plot for all planned visits.

12.7.4.4 Serum/Urine Pregnancy Test.

For subjects of childbearing potential, a pregnancy test will be performed on the day of enrollment and before any dose.

Pregnancy test results will be listed only.

12.7.5 Vital Signs

Vital signs will be summarized descriptively at each trial visit they are collected and by co-morbidity for SAS, including screening. Change from baseline values will be summarized for the post-vaccination visit. Vital

signs parameters to be summarized include systolic blood pressure (mmHg), diastolic blood pressure (mmHg), heart rate (bpm) and body temperature (°C).

If the temperature is collected in Fahrenheit convert using the following formula: ($^{\circ}\text{F} - 32$) $\times(5/9)$.

Vital signs will be listed as well.

12.7.6 Physical Examinations and ECGs

12.7.6.1 Physical Examinations

At specific trial visits a complete physical examination will be performed and the results collected if there are clinically significant results.

Physical examination results will be listed only.

12.7.6.2 Electrocardiogram

An electrocardiogram (ECG) with conventional 12-lead traces will be recorded on Day -7 for all subjects. Additionally, ECGs should be performed as clinically indicated.

ECG results will be listed only.

14.0 Glossary of Abbreviations

AE	Adverse event
AESI	Adverse event of special interest
ALP	Alkaline Phosphatase
ALT	Alanine Aminotransferase
aPTT	Activated Partial Thromboplastin Time
AST	Aspartate Aminotransferase
ATC	Anatomical Therapeutic Chemical
BMI	Body mass index
BUN	Urea Nitrogen
CEPI	Coalition for Epidemic Preparedness Innovations
CMI	Cell-mediated immunity
COPD	Chronic obstructive pulmonary disease
CoV	Coronavirus
CRP	C-Reactive Protein
CVnCoV	Investigational SARS-CoV-2 mRNA vaccine
DSMB	Data Safety Monitoring Board
ECG	Electrocardiogram
eCRF	Electronic case report form
ELISA	Enzyme-linked immunosorbent assay
FDA	United States Food and Drug Administration
GGT	Gamma Glutamyl Transferase
GM	Geometric mean
GMT	Geometric mean titer
GSD	Geometric standard deviation
Ig	Immunoglobulin
INR	Prothrombin Intl. Normalized Ratio
IS	Immunogenicity Set
iSRC	Internal Safety Review Committee
LDH	Lactate Dehydrogenase
MCH	Ery. Mean Corpuscular Hemoglobin
MCHC	Ery. Mean Corpuscular HBG Concentration
MCV	Ery. Mean Corpuscular Volume
MedDRA	Medical Dictionary for Regulatory Activities

mRNA	Messenger ribonucleic acid
N	Nucleocapsid
PCR	Polymerase chain reaction
pIMD	Potential immune-mediated disease
PPI	Per Protocol Immunogenicity Set
PT	Prothrombin Time
RBC	Erythrocytes
RBD	Receptor-binding domain
RNA	Ribonucleic acid
RT-PCR	Reverse transcription polymerase chain reaction
S	Spike
SAE	Serious adverse event
SAP	Statistical analysis plan
SARS	Severe acute respiratory syndrome
SARS-CoV-2	Severe acute respiratory syndrome coronavirus 2
SAS	Safety Analysis Set
SD	Standard deviation
SGPT	Alanine Aminotransferase
SGOT	Aspartate Aminotransferase
SMQ	Standardized MedDRA Queries
SOC	System Organ Class
TBD	To be determined
TFL	Tables Figures Listings
WBC	Leukocytes
WHO	World Health Organization
WHODRUG	WHO Drug Dictionary

15.0 Appendices

Appendix 1 Potential Immune-Mediated Diseases

Current list of pIMDs:

Gastrointestinal disorders:

- o Celiac disease
- o Crohn's disease
- o Ulcerative colitis
- o Ulcerative proctitis

Liver disorders:

- o Autoimmune cholangitis
- o Autoimmune hepatitis
- o Primary biliary cirrhosis
- o Primary sclerosing cholangitis

Metabolic diseases:

- o Addison's disease
- o Autoimmune thyroiditis (including Hashimoto thyroiditis)
- o Diabetes mellitus type I
- o Grave's or Basedow's disease

Musculoskeletal disorders:

- o Antisynthetase syndrome
- o Dermatomyositis
- o Juvenile chronic arthritis (including Still's disease)
- o Mixed connective tissue disorder
- o Polymyalgia rheumatic
- o Polymyositis
- o Psoriatic arthropathy
- o Relapsing polychondritis
- o Rheumatoid arthritis
- o Scleroderma, including diffuse systemic form and CREST syndrome
- o Spondyloarthritis, including ankylosing spondylitis, reactive arthritis (Reiter's Syndrome) and undifferentiated spondyloarthritis
- o Systemic lupus erythematosus
- o Systemic sclerosis

Neuro-inflammatory disorders:

- o Acute disseminated encephalomyelitis, including site specific variants (e.g., non-infectious encephalitis, encephalomyelitis, myelitis, myeloradiculomyelitis)
- o Cranial nerve disorders, including paralyses/paresis (e.g., Bell's palsy)
- o Guillain-Barré syndrome, including Miller Fisher syndrome and other variants
- o Immune-mediated peripheral neuropathies, Parsonage-Turner syndrome and plexopathies, including chronic inflammatory demyelinating polyneuropathy, multifocal motor neuropathy, and polyneuropathies associated with monoclonal gammopathy
- o Multiple sclerosis
- o Narcolepsy
- o Optic neuritis
- o Transverse Myelitis

Skin disorders:

- o Alopecia areata
- o Autoimmune bullous skin diseases, including pemphigus, pemphigoid and dermatitis herpetiformis
- o Cutaneous lupus erythematosus
- o Erythema nodosum
- o Morphoea
- o Lichen planus
- o Psoriasis
- o Sweet's syndrome
- o Vitiligo

Vasculitides:

- o Large vessels vasculitis including: giant cell arteritis such as Takayasu's arteritis and temporal arteritis
- o Medium sized and/or small vessels vasculitis including: polyarteritis nodosa, Kawasaki's disease, microscopic polyangiitis, Wegener's granulomatosis, Churg-Strauss syndrome (allergic granulomatous angiitis), Buerger's disease thromboangiitis obliterans, necrotizing vasculitis and anti-neutrophil cytoplasmic antibody (ANCA) positive vasculitis (type unspecified), Henoch-Schonlein purpura, Behcet's syndrome, leukocytoclastic vasculitis

Others:

- o Antiphospholipid syndrome
- o Autoimmune hemolytic anemia
- o Autoimmune glomerulonephritis (including IgA nephropathy, glomerulonephritis rapidly progressive, membranous glomerulonephritis, membranoproliferative glomerulonephritis, and mesangioproliferative glomerulonephritis)
- o Autoimmune myocarditis/cardiomyopathy
- o Autoimmune thrombocytopenia
- o Goodpasture syndrome
- o Idiopathic pulmonary fibrosis
- o Pernicious anemia
- o Raynaud's phenomenon
- o Sarcoidosis
- o Sjögren's syndrome
- o Stevens-Johnson syndrome
- o Uveitis

Appendix 2 Adverse Events of Special Interest for SARS-CoV-2 Vaccines

Current list of AESIs (based on Brighton Collaboration via CEPI's Safety Platform for Emergency vACCines [SPEAC] Project):

Immunological disorders:

- o Anaphylaxis
- o Vasculitides
- o Enhanced disease following immunization
- o Multisystem inflammatory syndrome in children

Respiratory disorders:

- o Acute respiratory distress syndrome
- o COVID-19 disease

Cardiac disorders:

Acute cardiac injury including:

- o Microangiopathy
- o Heart failure and cardiogenic shock
- o Stress cardiomyopathy
- o Coronary artery disease
- o Arrhythmia
- o Myocarditis, pericarditis

Hematological disorders:

- o Thrombocytopenia

Coagulation disorder:

- o Deep vein thrombosis
- o Pulmonary embolus
- o Cerebrovascular stroke
- o Limb ischemia
- o Hemorrhagic disease

Renal disorders:

- o Acute kidney injury

Gastrointestinal disorders

- o Liver injury

Neurological disorders:

- o Generalized convulsion
- o Guillain-Barré Syndrome
- o Acute disseminated encephalomyelitis
- o Anosmia, ageusia
- o Meningoencephalitis

Dermatologic disorder:

- o Chilblain-like lesions
- o Single organ cutaneous vasculitis
- o Erythema multiforme

Other:

- o Serious local/systemic adverse reaction following immunization

** These are generally the conditions one encounters in normal subjects as AESI, but in this trial we use comorbid subjects and some of them may have coronary disease, arrhythmias or myocarditis to start with.

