#### 4.2.1 Primary

##### Safety

- The frequency, intensity, and duration of solicited local AEs on each vaccination day and the following 7 days.
- The frequency, intensity, duration, and relationship to trial vaccination of solicited systemic AEs on each vaccination day and the following 7 days.
- The occurrence, intensity and relationship to trial vaccination of unsolicited AEs on each vaccination day and the following 28 days.
- The occurrence and relationship to trial vaccination of SAEs and AESIs throughout the trial.

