#### **9.1.1.3 Adverse Events of Special Interest**

The following events will be considered as AESIs during this trial:

- AEs with a suspected immune-mediated etiology (pIMDs, see Appendix 7).
- Other AEs relevant to SARS-CoV-2 vaccine development or the target disease (see Appendix 8 for the current list of AESIs and see Section 9.3 for details on laboratory testing for COVID-19).
- Non-serious intercurrent medical conditions that may affect the immune response to vaccination will also be collected throughout the trial.

AESIs will be collected throughout the trial.

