### **Immunological disorders:**

- Anaphylaxis
- Vasculitides
- Enhanced disease following immunization
- Multisystem inflammatory syndrome in children
- Subacute thyroiditis

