### **Gastrointestinal disorders**

- Liver injury
- Pancreatitis

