**Other:**

- Serious local/systemic adverse reaction following immunization
- Rhabdomyolysis

\*\* These are generally the conditions one encounters in normal subjects as AESI, but in this trial we use comorbid subjects and some of them may have coronary disease, arrhythmias or myocarditis to start with.

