9.4 Estimands

Based on the Protocol Amendment #1, a subset of endpoints will be presented. See Section 6.1, 6.2, 6.3 and 6.4 and Appendix 4 List of Abbreviated Scope Based on SAP Version 2.0 for additional details.

ENDPOINTS (subject level)	ESTIMANDS (population level)
Primary Safety	

The frequency, intensity, and duration of solicited local AEs on each vaccination day and the following 7 days.
 
The frequency, intensity, duration, and relationship to trial vaccination of solicited systemic AEs on each vaccination day and the following 7 days.
 
The occurrence, intensity and relationship to trial vaccination of unsolicited AEs on each vaccination day and the following 28 days.
 
The occurrence and relationship to trial vaccination of SAEs and AESIs throughout the trial.
	
In subjects who received at least one dose of CVnCoV vaccine and a post baseline vaccine safety assessment is available. Subjects receiving an authorized/licensed COVID-19 vaccine during the course of the trial will be censored at the day after intake. The primary safety will be analyzed with the safety analysis set.
 
The number and percentage of subjects overall and by co-morbidity:
 
Each solicited local AE within 7 days (after each trial vaccination by intensity and overall).
 
Each solicited systemic AE within 7 days after each trial vaccination by intensity, by relationship to trial vaccine and overall.
 
The mean duration in days by group with standard deviation of solicited AEs (within the solicited period, total duration).
 
At least 1 unsolicited AEs, at least 1 grade unsolicited AEs and each unsolicited AEs by SOC/PT occurring within 28 days after each trial vaccination and overall by causal relationship to trial vaccine and overall.
 
At least 1 SAE, or at least 1 AESI to vaccine overall by causal relationship to trial vaccine and overall.

ENDPOINTS (subject level)	ESTIMANDS (population level)
Primary Immunogenicity	

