10.7.4 Adverse Events of Special Interest (AESI)

The following events will be considered as AESIs during this trial:

- AEs with a suspected immune-mediated etiology (see Appendix 1 Potential Immune-Mediated Diseases).
- Other AEs relevant to SARS-CoV-2 vaccine development or the target disease (see Appendix 2 for the current list of AESIs and see the protocol for details on laboratory testing for COVID-19).
- Non-serious intercurrent medical conditions that may affect the immune response to vaccination will also be collected throughout the trial.

AESIs will be collected throughout the trial.

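### The SAP's AESI list omits three conditions that the protocol's list contains, so a primary safety endpoint is defined differently in the two documents

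*SAP*

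**What the plan says.** Protocol 4.2.1 makes this a primary safety endpoint: "The occurrence and relationship to trial vaccination of SAEs and AESIs throughout the trial". SAP 9.4 carries the endpoint over and gives the population-level summary as "At least 1 SAE, or at least 1 AESI to vaccine overall by causal relationship to trial vaccine and overall".

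Both documents define an AESI in three parts: events of suspected immune-mediated origin, other events relevant to SARS-CoV-2 vaccines or to COVID-19, and non-serious intercurrent conditions that could affect the immune response. For the second part, protocol 9.1.1.3 sends the reader to the protocol's own list ("see Appendix 8 for the current list of AESIs and see Section 9.3"). SAP 10.7.4 sends the reader to a different one ("see Appendix 2 for the current list of AESIs") and refers back to the protocol only for COVID-19 laboratory testing.

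Protocol Appendix 8 includes "Subacute thyroiditis" under immunological disorders, "Pancreatitis" under gastrointestinal disorders and "Rhabdomyolysis" under other. None of these is in the SAP's list, which is headed "Appendix 2 Adverse Events of Special Interest for SARS-CoV-2 Vaccines".

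AESI reporting survives the reduced scope. SAP 6.4 keeps it among the key safety analyses, SAP 12.7.1.1 puts AESIs and related AESIs in the overall summary, and SAP Appendix 4 retains Table 14.3.2.26.1.

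**The concern.** A primary safety endpoint should have one definition. Sites identify and report AESIs from the protocol. Protocol Appendix 9 requires AESIs to be reported on the same form and to the same timelines as serious adverse events. An analyst working from the SAP alone has a shorter list. An event that a site correctly reports as an AESI could therefore fall outside the SAP's definition, and the AESI table could then disagree with the safety report forms.

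If the mismatch is found only after the events are known, someone has to decide then whether a particular event counts. A pre-specified definition is meant to avoid that.

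**Working it through.** The plan gives no figure to reproduce. The check compares two lists, treating the SAP's entry for COVID-19 disease and the protocol's entry for COVID-19 as the same term.

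| Heading | Protocol Appendix 8 | SAP Appendix 2 | In protocol only |
|---|---|---|---|
| Immunological | 5 | 4 | subacute thyroiditis |
| Respiratory | 2 | 2 | none |
| Cardiac | 6 | 6 | none |
| Hematological | 1 | 1 | none |
| Coagulation | 5 | 5 | none |
| Renal | 1 | 1 | none |
| Gastrointestinal | 2 | 1 | pancreatitis |
| Neurological | 5 | 5 | none |
| Dermatologic | 3 | 3 | none |
| Other | 2 | 1 | rhabdomyolysis |
| **Total** | **32** | **29** | **3** |

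The difference is 32 − 29 = 3 terms, and no term is in the SAP only. Each missing term comes from a heading that is otherwise intact in the SAP, so this does not look like damaged or redacted text.

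**Are the terms recovered elsewhere in the SAP?** SAP Appendix 1 (potential immune-mediated diseases) names none of the three. Its nearest entry is autoimmune thyroiditis, which is a different named condition.

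**Is the shorter list explained?** It is not mentioned in the SAP change history, in SAP 6.3 or 6.4, or in the description of changes in the protocol amendment. SAP 6.0 says the SAP is to be read with protocol version 2.0 and the amendment.

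**What happens to such an event?** There are two cases, and the SAP does not say which applies.

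- *AESIs classified by the SAP definition.* The event is left out of Table 14.3.2.26.1 and of the AESI rows in the overall summary. Once recorded, it still appears in the whole-trial unsolicited event table (14.3.2.17.1), in Listing 16.2.7.1 and, if serious, in Listing 16.2.7.5. It is misclassified, not lost.
- *AESIs taken from the investigator's report under the protocol.* The event is counted as an AESI and the outputs are correct, although the SAP's written definition is still wrong.

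**Size.** SAP 6.3 bases the analysis on 129 subjects. Assume that all 129 are in the Safety Analysis Set and that one subject has one of the three conditions and no other AESI. In the first case the number of subjects with at least one AESI is then one too low, which is 1/129 = 0.8 percentage points overall. Within a co-morbidity stratum the shift would be larger, but the documents do not give the stratum sizes. They also give no expected rate for these conditions, so no expected count can be calculated.

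**The case against.** The strongest reply is that the consequence is not established. The SAP nowhere says that AESI tables are built by matching coded terms to Appendix 2. Where it does derive event groups from terms it says so: SAP 10.7.7 describes filtering by standardised MedDRA queries, and Appendix 3 lists preferred terms for the two customised queries. Appendix 2 has no preferred terms, and some entries, such as enhanced disease after immunisation, could hardly be programmed as a match. It may be no more than a descriptive list, with the investigator's report driving the tables. SAP 10.7.4 also has three parts, and a serious case judged to be a reaction to vaccination might enter through the Appendix 2 entry for serious reactions. Finally, the analysis is descriptive, covers 129 subjects and feeds an abbreviated report.

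Most of this stands. A reader might infer from the shorter list that the three conditions would be counted as zero AESIs whatever occurred, or would vanish from the safety report. The documents do not support either inference. The first requires a classification rule that the SAP does not state. The second is contradicted by the unsolicited event tables and the listings.

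The objection does not remove the contradiction itself. SAP 10.7.4 calls Appendix 2 the current list, the protocol gives that status to a longer list, and nothing explains the difference.

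**Conclusion.** The point holds as an unexplained inconsistency between protocol and SAP in the definition of a primary safety endpoint whose output is retained. Its extent is exact: three of 32 protocol terms are missing and nothing is added.

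The effect on the tables is conditional. Such an event drops out of the AESI outputs only if classification follows the SAP definition; if the investigator's report is used, it is counted. The numerical impact is likely to be small with 129 subjects, and no formal inference depends on it. The correction is worth making because it is nearly free and removes a choice that could otherwise be made with the events in view.

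**What to change.** Before database lock, restore subacute thyroiditis, pancreatitis and rhabdomyolysis to SAP Appendix 2 so that it matches protocol Appendix 8. Add one sentence to SAP 10.7.4 or 12.7.1.1 stating that Table 14.3.2.26.1 and the AESI rows of the overall summary use the protocol's AESI definition, so that an AESI reported under the protocol is counted as one. Record the change in the SAP change history.

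Nothing further is needed. In particular, the inconsistency does not call for an extra rule that counts any event matching a listed term regardless of the investigator's report. Both appendices note that some subjects may have coronary disease, arrhythmias or myocarditis at the start, and such a rule could label events as AESIs that the investigator did not report as such.

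The cost is three lines in an appendix, one sentence in the text and a change-log entry. No new data are needed, and the analyses outside the AESI outputs are unaffected.

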Appendix 3 MedDRA Terms for CMQs

MedDRA Version 24.1

A. Customized MedDRA Queries related to taste and smelling disorder

Preferred Term
Ageusia
Anosmia
Dysgeusia
Hypergeusia
Hypogeusia
Hyposmia
Parosmia
Taste disorder

B. Customized MedDRA Querie related to paraesthesia, hypoesthesia, and hyperesthesia

Preferred Term
Anal hypoesthesia
Anal paraesthesia
Dental paraesthesia
Eye paraesthesia
Genital hyperesthesia
Genital hypoesthesia
Genital paraesthesia
Hemihyperesthesia
Hemiparaesthesia
Hyperesthesia
Hyperesthesia eye
Hyperesthesia teeth
Hypoesthesia
Hypoesthesia eye
Hypoesthesia oral
Hypoesthesia teeth
Intranasal hypoesthesia
Intranasal paraesthesia
Oral hyperesthesia
Paraesthesia
Paraesthesia ear
Paraesthesia mucosal
Paraesthesia oral

Pharyngeal hypoesthesia

Pharyngeal paraesthesia

Thermohyperraesthesia

Thermohypoesthesia

Appendix 4 List of Abbreviated Scope Based on SAP Version 2.0

14.1 Demographic Data Tables
Table 14.1.1.1 Subject Analysis Sets (All Subjects)
Table 14.1.1.2 Enrollment by Country and Center (Safety Analysis Set)
Table 14.1.1.3 Subject Disposition (Safety Analysis Set)
Table 14.1.2.1 Demographic Characteristics (Safety Analysis Set)
Table 14.1.3.1 Medical History by System Organ Class and Preferred Term (Safety Analysis Set)
Table 14.1.4.1 Prior Medications by ATC Classification and WHO Drug Dictionary Preferred Term (Safety Analysis Set)
Table 14.1.5.1 Concomitant Medications by ATC Classification and WHO Drug Dictionary Preferred Term (Safety Analysis Set)
Table 14.1.6.1 Summary of Important Protocol Deviation Data (Safety Analysis Set)
Table 14.1.7.1 Licensed/authorized Vaccine Application after Dose 1 (Safety Analysis Set)
14.2 Immunogenicity
Table 14.2.1.1 Seroconversion Rate for SARS-CoV-2 RBD Antibodies (IgG) by Time Point (Per Protocol Immunogenicity Set)
Table 14.2.2.1 Summary of SARS-CoV-2 RBD Antibodies (IgG) by Time Point (Per Protocol Immunogenicity Set)
Table 14.2.3.1 Seroconversion Rate for SARS-CoV-2 neutralizing Antibodies MN 25 TCID50 by Time Point (Per Protocol Immunogenicity Set)
Table 14.2.4.1 Summary of SARS-CoV-2 neutralizing Antibodies MN 25 TCID50 in Serum at Day 43 (Per Protocol Immunogenicity Set)
Table 14.2.6.1 Subjects with Asymptomatic SARS-CoV-2 infection as measured with retrospective Serology on Day 1, 43, 120 (Per Protocol Immunogenicity Set)
14.3 Safety Data Tables
14.3.1 Exposure Table
Table 14.3.1.1 Summary of Exposure (Safety Analysis Set)
14.3.2 Adverse Events Data Tables
Table 14.3.2.1.1 Overall Summary of Adverse Events (Safety Analysis Set)
Table 14.3.2.2.1 Summary of Solicited Adverse Events and Maximum Grade Occurring on the Day of Vaccination and the following 7 Days after any Dose (Safety Analysis Set)
Table 14.3.2.3.1 Local Solicited Adverse Events and Maximum Grade Occurring on the Day of Vaccination and the following 7 Days after any Dose (Safety Analysis Set)
Table 14.3.2.4.1 Systemic Solicited Adverse Events and Maximum Grade Occurring on the Day of Vaccination and the following 7 Days after any Dose (Safety Analysis Set)
Table 14.3.2.6.1 Duration of Solicited Adverse Events Occurring on the Day of Vaccination and the following 7 Days after any Dose (Safety Analysis Set)

Table 14.3.2.16.1 Unsolicited Adverse Events by System Organ Class and Preferred Term Occurring on the Day of Vaccination and the following 28 Days after any Dose (Safety Analysis Set)
Table 14.3.2.16.2 Unsolicited Adverse Events by System Organ Class and Preferred Term Occurring on the Day of Vaccination and the following 28 Days after Dose 1 (Safety Analysis Set)
Table 14.3.2.16.3 Unsolicited Adverse Events by System Organ Class and Preferred Term Occurring on the Day of Vaccination and the following 28 Days after Dose 2 (Safety Analysis Set)
Table 14.3.2.17.1 Unsolicited Adverse Events for Duration of Trial by System Organ Class and Preferred Term (Safety Analysis Set)
Table 14.3.2.17.2 Related Unsolicited Adverse Events for Duration of Trial by System Organ Class and Preferred Term (Safety Analysis Set)
Table 14.3.2.20.1 Unsolicited Adverse Events by System Organ Class, Preferred Term, and Maximum Severity Occurring on the Day of Vaccination and the following 28 Days after any Dose (Safety Analysis Set)
Table 14.3.2.20.2 Unsolicited Adverse Events by System Organ Class, Preferred Term, and Maximum Severity Occurring on the Day of Vaccination and the following 28 Days after Dose 1 (Safety Analysis Set)
Table 14.3.2.20.3 Unsolicited Adverse Events by System Organ Class, Preferred Term, and Maximum Severity Occurring on the Day of Vaccination and the following 28 Days after Dose 2 (Safety Analysis Set)
Table 14.3.2.26.1 Adverse Events of Special Interest for Duration of Trial by System Organ Class and Preferred Term (Safety Analysis Set)
Table 14.3.2.29.1 Adverse Events Leading to Study Withdrawal by System Organ Class and Preferred Term (Safety Analysis Set)
Table 14.3.2.30.1 Adverse Events Leading to Vaccine Withdrawal by System Organ Class and Preferred Term (Safety Analysis Set)
